6.5 Economic analysis

The type and extent of economic evaluation will crucially depend upon the clinical outcome of the trial:

- (i) If vitamin D and calcium are shown to reduce fractures in equal amounts compared with the placebo, vitamin D will be the preferred therapy on cost grounds. Given the lower cost of vitamin D, it is very likely that resource savings will occur. Thus, the economic evaluation will mainly consist of quantifying the cost savings that will accrue in order to encourage implementation of the research findings.
- (ii) If vitamin D alone is ineffective but calcium alone or in combination is effective, this may lead to a net cost to society. If this proves to be the case we will estimate the incremental cost per fracture prevented and per quality adjusted life year (QALY) gained.

(iii) If vitamin D is effective alone but is even more effective in combination with calcium then, again, the extra cost per fracture prevented and per QALY will be estimated to aid a decision about whether the additional effectiveness gained from the addition of calcium is worthwhile.

The underlying aim is to keep economic data collection as parsimonious as possible to minimise the burden for this elderly population.

Outcome Data

To generate a cost per QALY, data on utility or health gain are required and these will be gathered primarily using the EQ-5D. However, the EQ-5D is a relatively insensitive measure, particularly for the less severe fracture categories (eg Colles' fracture). The SF12 will therefore also be used to assist in estimating the utility values from the less disabling fractures.

Cost Data

The acquisition costs of calcium and vitamin D can be simply ascertained from published sources (eg MIMS), and different prices from different suppliers will be used in a sensitivity analysis.

To elicit subsequent costs two main methods will be used. Midway through the trial a questionnaire survey of all study participants will be used to describe subsequent costs (Appendix 12). This will provide data on use of NHS-funded resources, such as general practitioners', hospital doctors' and other NHS professionals' time, together with non-NHS resource use, such as contacts with social services, privately funded help and more informal care. Those who have had a further fracture will be divided into those who had fractured recently, those who have fractured in the previous 1 to 6 months, and those who fractured more than 6 months previously. They will be compared with the surveyed participants who have not fractured again, but who were recruited at the same time. Data on these representative (sub-) groups will be used as a basis for modelling such resource use amongst the study groups.

Whilst certain costs will increase should a patient return home after fracture (such as home help) the dominant cost is likely to be that incurred when a patient has to go into long-term care as a result of a fracture. This information on location and duration of care will be collected at each follow-up contact (i.e. every four months).

With respect to price data, published price estimates will be used. Two detailed studies of hospital hip fracture costs have been undertaken in Aberdeen and Cambridge ^{19,20}. When these studies have been adjusted to a common length of stay they give similar estimates (£4018 and £4808 per hip fracture). Therefore, these costs will be used to price acute hospital episodes of care for hip fracture. For Colles fracture, costs from a recently published costing study of osteoporotic fractures will be used². For vertebral fractures, at some point in the trial, the incidence of clinically significant fractures amongst the whole study population will be calculated. If this incidence is sufficiently high to affect the relative costs of the interventions, a separate costing study of such fractures will be carried out. For other items of resource use, such as general practitioner consultations, social services and long-stay care we will use the price estimates generated by the Personal and Social Services Research Unit²¹. For visits to hospital doctors, we will use published tariffs for the cost of outpatient visits as a basis of estimation.

Finally, modelling will be used to extend the analysis beyond the time course of the trial.

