7. SAMPLE SIZE AND FEASIBILITY

7.1 Sample size sought

The aim is to recruit about 6,500 people to the trial. This is based on a wish to identify a reduction of one fewer person per hundred allocated an active treatment sustaining a fracture each year over a median period of three years, if this was the true effect. Based on data from published trials in similar contexts the anticipated all fracture rate in the control groups is 15%. A total of 4000 participants would be needed in the analysis to have 80% power (2P<0.05) to detect an overall reduction to 12%. If the true effect is somewhat larger, say a 4% absolute benefit, the power will be over 90%. A trial of this size also has over 80% power to identify a 2% absolute difference in hip fracture rates (from 6% to 4%, or 5% to 3%).

The numbers sought have been inflated to 6,500 to take account of losses to followup. The main reason for 'loss to follow up' will be death. In the large Dutch trial¹² the rate was about 20% over three years, but we expect it to be higher overall (about 30%) because some of our participants will have sustained a recent proximal femoral fracture. Losses for other reasons, principally moving to other areas, are estimated from observations in one participating centre to be about 5%. The sample size has therefore been inflated by 35%.

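### The fracture verdict selects the economic analysis, and a finding of equal effect names vitamin D as preferred, although near-equality of vitamin D and calcium cannot be shown at the planned size.

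*Protocol*

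**What the plan says.** Protocol Section 6.5 opens with a conditional plan: "The type and extent of economic evaluation will crucially depend upon the clinical outcome of the trial". Three cases follow.

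- **Case (i).** Vitamin D and calcium are both "shown to reduce fractures in equal amounts compared with the placebo, vitamin D will be the preferred therapy on cost grounds". The evaluation is then mainly a quantification of savings.
- **Case (ii).** "If vitamin D alone is ineffective but calcium alone or in combination is effective", the incremental cost per fracture prevented and per QALY is estimated.
- **Case (iii).** If vitamin D works alone and the combination works better still, the same incremental ratios are estimated for adding calcium.

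The section gives no margin, interval rule or test for equal amounts.

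Section 7.1 gives the size: "The aim is to recruit about 6,500 people to the trial", with a control rate stated as "the anticipated all fracture rate in the control groups is 15" per cent, and "A total of 4000 participants would be needed in the analysis to have 80% power (2P<0.05) to detect an overall reduction to 12" per cent. Section 6.1 lists the two factorial margins and the four-group comparison as principal comparisons. Section 7.1 gives no power or precision for single arms.

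**The concern.** A verdict of equal effect is a claim that a difference is small. It needs a margin and enough precision to place the difference inside it. Here the verdict settles two things in advance: which agent is preferred, and whether an incremental analysis is promised at all. If the data cannot separate equal from moderately different, the step from equal to cheapest replaces the trade-off that an economic evaluation exists to quantify. A real difference in fractures prevented could be left out of the comparison with price. Section 1.3 gives cost-effectiveness and resource implications among the reasons for the trial, so this is not a marginal output.

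**Working it through.** **Inputs.** From Section 7.1: control rate 15%, treated rate 12%, 4000 analysed, two-sided 0.05, 6,500 recruited, 35% losses. From Section 3.2: four groups. Assumed: equal allocation, since no ratio is stated. This gives 4000/4 = 1000 analysed per arm. Applying the stated losses to the target gives 6500 × 0.65 = 4225, or 1056 per arm. Counting everyone randomised gives 6500/4 = 1625 per arm, the most favourable figure.

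**The plan's own figure.** Power = Φ{[Δ − 1.96√(2p̄(1−p̄)/n)] / √(p₁(1−p₁)/n + p₂(1−p₂)/n)}. With n = 2000, Δ = 0.03 and p̄ = 0.135, this is Φ[(0.03 − 0.0212)/0.0108] = 79.3%. Solving for 80% gives 2036 per group, 4072 in total, against the stated 4000. For 15% v 11%, power is 96.4%, in line with the claim that for a larger effect, "say a 4% absolute benefit, the power will be over 90" per cent. The statements reproduce, but only at 2000 v 2000, the factorial margins.

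**What pooling does for vitamin D against calcium.** Let a, b, c, d be the risks on combination, vitamin D, calcium and placebo. The vitamin D main effect is [(a+b) − (c+d)]/2 and the calcium main effect is [(a+c) − (b+d)]/2. Their difference is b − c. The factorial design adds no precision to this contrast.

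**Precision of b − c.** Half-width = 1.96√(2p(1−p)/n).

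| p | n = 1000 | n = 1625 |
|---|---|---|
| 12% | 2.8 points | 2.2 points |
| 13.5% | 3.0 points | 2.3 points |
| 15% | 3.1 points | 2.5 points |

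The whole planned effect is 3 points.

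**Chance of showing equivalence.** Take both agents truly at 12% and require the 90% interval to lie inside a margin m. Power = 2Φ(m/SE − 1.645) − 1, or 0 if negative, with SE = √(2 × 0.12 × 0.88/n), which is 0.0145 at 1000 and 0.0114 at 1625. The protocol gives no margin, so a range is shown.

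| Margin (assumed) | n = 1000 | n = 1625 |
|---|---|---|
| 1.5 points | 0% | 0% |
| 2 points | 0% | 9% |
| 3 points | 33% | 68% |

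For 80% power, a 1.5-point margin (half the planned effect) needs 0.2112 × (1.645 + 1.282)²/0.015², about 8,040 per arm. A 3-point margin needs about 2,010 per arm.

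**How case (i) could behave.** Assume true rates of 15% on placebo, 12% on vitamin D and 10% on calcium, and read equal as not significantly different. For b v c alone at 1000 per arm, SE = √(0.12 × 0.88/1000 + 0.10 × 0.90/1000) = 0.0140 and 0.02/0.0140 = 1.43, so the comparison is non-significant in about 70% of trials. Case (i) also needs both agents to beat placebo. That condition favours trials in which vitamin D happened to do well, so the proportion rises. By simulation of independent binomial arms with two-sided 5% tests, among trials in which both beat placebo the direct comparison is non-significant in about 84% at 1000 per arm and 65 to 66% at 1625. These are conditional figures. Both agents beat placebo in about 49% and 71% of trials, so case (i) would apply in about 0.49 × 0.84 = 41% and 0.71 × 0.65 = 46% of all trials.

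**The case against.** **A stronger harm might be inferred.** If one agent gave the full 3 points and the other nothing, b v c would be non-significant about half the time at 1000 per arm (power 50.1%). A reader might conclude that a wholly ineffective agent would be named as preferred that often. The protocol does not support this. Case (i) requires both agents to be shown to reduce fractures against placebo, so a null agent would need a false positive first. Simulating placebo 15%, vitamin D 15% and calcium 12% meets both conditions in about 2% of trials, at 1000 or 1625 per arm. With a partial difference (vitamin D 1.5 points, calcium 3 points) they are met in about 12% of trials at 1000 and 19% at 1625.

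**Equal need not mean not significant.** This is correct. The section gives no test, and a later analysis plan could supply a margin. But the rule that links the verdict to the analysis is fixed in the protocol, and the planned numbers could not support a useful margin.

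**Ineffective can be read from the margin.** This holds in part. Without interaction, the vitamin D effect comes from about 2000 v 2000 at about 79% power, although the text speaks of vitamin D alone. The argument does not extend to equal, because b − c gains nothing from pooling.

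**1000 per arm is the least favourable count.** Section 6.1 includes everyone with data in time-to-event analyses, so 1625 is shown beside it. It is generous, because people who die early contribute only part of the follow-up.

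**Nothing forbids a fuller analysis in case (i).** The text says that counting savings is the main content, not the only content, and a price sensitivity analysis is planned. So uncertainty about effect is not necessarily thrown away. What stands is that no incremental analysis is promised there.

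**At equal effect, the cheaper option is preferred.** This is close to a truism. The difficulty is that this trial cannot show the premise.

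**Conclusion.** The point holds for case (i). The protocol ties the choice of economic analysis, and a preferred agent, to a verdict of equal effect that the trial is not sized to give. The contrast that decides it has a 95% half-width of 2.8 to 3.1 points at 1000 per arm, or 2.2 to 2.5 points at 1625, against a planned effect of 3. Equivalence within half that effect cannot be shown at either size. In the assumed 15%, 12%, 10% scenario, a 2-point difference would pass as equal in about 84% (1000 per arm) or about two thirds (1625 per arm) of trials in which both agents beat placebo.

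This rests on equal allocation, on the protocol's planning rates, on the assumed calcium rate and, for the last figures only, on reading equal as not significantly different. The point concerns the economic section. The primary fracture analysis and its sample size are unaffected.

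**What to change.** Replace the three conditional cases in Section 6.5 with one rule. Whatever the clinical verdict, estimate incremental costs, fractures and QALYs for all four groups, and report them with their joint uncertainty, for example by bootstrap with acceptability curves or net benefit. Remove the preferred agent named in advance, or let the preference follow from that analysis. If the word equal is kept, tie it to a stated margin and an interval rule, and acknowledge the precision available for b − c.

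The data are already planned: health status forms for all participants (Section 4.4), a resource-use questionnaire to all participants and care location at each four-monthly contact (Section 6.5). Participant burden does not rise. The cost is new wording and modest extra analysis. The downside is that a simple cost-saving headline may not be available.

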6.2 Measures of outcome

The principal clinical outcome measure is:

• all new low-energy fractures (other than face or skull) or clinical, radiologicallysupported, vertebral fractures reported.

Any apparent differences in fracture rates will be explored by subdivision into: proximal femoral, other lower limb/pelvis, distal forearm, other arm, clinical vertebral, and other fractures.

Other secondary outcome measures are:

- New radiologically-confirmed fractures
- Death after trial entry; the possible link between death and fracture will be examined in analyses of deaths occurring within three months of a new fracture
- General health status as measured by SF-12 and EQ-5D
- Hospital admissions after trial entry (number, length, place, and association with fracture)
- Change of residence category
- Falls (within five one-week window periods)
- Possible adverse effects (e.g. renal stones, gastrointestinal symptoms)
- New cancer registrations (Total, colon, breast, other)
- Deaths attributed to cardiovascular or cerebrovascular disease
- New cases of diabetes, taking oral hypoglycaemics and/or insulin

The ways in which these data will be displayed in the final report are illustrated in Appendix 11.

It is anticipated that other variables, such as bone density, genetic polymorphisms, and balance will be measured in explanatory studies and these will be described in separate protocols.

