The incidence of adverse effects from the proposed dosage of vitamin D and calcium is anticipated to be very low - in the systematic review renal insufficiency or stones were reported for 4/4025 (0.1%) and gastro-intestinal disturbances for 93/3892 (2.4%).

Collaborators and participants may write to the chairman of the steering committee about any worries they may have about the trial. If concerns arise about particular side-effects or about particular types of participants, these will be relayed to the Chairman of the Data Monitoring Committee.

If clinically indicated, rapid unblinding of trial materials will be available through the trial office.

The Multicentre Research Ethics Committee for Scotland has approved the trial. The trial will be conducted according to the MRC Good Clinical Practice Guidelines (1998)²².

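### Survey resource use reaches the randomised groups by one stated route, fracture status; with no stated comparison by allocation, differences in non-fracture care almost cancel from the modelled cost difference

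*Protocol*

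**What the plan says.** Protocol section 6.5 (Cost Data) sets out the survey: "Midway through the trial a questionnaire survey of all study participants will be used to describe subsequent costs". It covers NHS professional time, social services, paid help and informal care.

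The section then fixes how the answers are grouped. "Those who have had a further fracture will be divided into those who had fractured recently", with two further groups by longer time since fracture. "They will be compared with the surveyed participants who have not fractured again, but who were recruited at the same time". The step to the randomised groups follows: "Data on these representative (sub-) groups will be used as a basis for modelling such resource use amongst the study groups". Allocation does not appear as a comparison variable, and no driver of resource use other than fracture and its timing is named.

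The acute hospital prices named are for hip fracture, Colles fracture and, if incidence warrants it, vertebral fracture. General unit costs are named for GP consultations, social services, long-stay care and outpatient visits. Location and duration of care are collected every four months.

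Elsewhere, section 6.1 bases the analyses on everyone randomised. Section 6.2 lists hospital admissions and possible adverse effects as outcomes. Section 4.5 asks general practitioners to report renal insufficiency, renal stones and hypercalcaemia.

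**The concern.** A contrast of re-fractured with un-fractured people is observational. It answers what a fracture costs, not what allocation to a tablet costs. If each study group's survey-type cost is built from pooled fracture-status means, allocation can alter that cost essentially only by altering the number of fractures.

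The trial looks for effects that do not act through fracture, and 6.5 gives them no route into the cost difference. Scenarios (ii) and (iii) of 6.5 promise an incremental cost per fracture prevented and per QALY. Leaving out the cost of harms caused by the supplements would make those ratios look better than they are. This bears particularly on the extra cost of adding calcium in (iii), where any calcium-specific harm belongs in the increment.

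**Working it through.** **Inputs from the protocol**
- Fracture rates 15% and 12% (7.1).
- Review rates for gastrointestinal disturbance, 93/3892, and for renal insufficiency or stones, 4/4025 (8.3).
- Acute hip fracture prices £4018 and £4808 (6.5).
- A 2% absolute difference in hip fracture, used for power (7.1).

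**Assumed, because the protocol gives no figure**
- Survey-type cost per fracture F = £1000.
- Excess adverse-effect rate a on active tablets, 1% to 10%.
- Cost per adverse effect c, £50 to £300.
- Adverse effects independent of fracture, and two equal groups.

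**1. The protocol's rates reproduce.** 93/3892 = 2.39% and 4/4025 = 0.10%, or about 24 and 1 per 1000.

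**2. The two methods.** Let p0 and p1 be the fracture rates in the control and active groups.
- By allocation: D_B = (p1 − p0)F + ac.
- From pooled fracture-status means: the fractured mean carries ac × p1/(p0 + p1) and the un-fractured mean carries ac × (1 − p1)/(2 − p0 − p1). Hence D_A = (p1 − p0) × {F + ac × [p1/(p0 + p1) − (1 − p1)/(2 − p0 − p1)]}.

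With p0 = 0.15 and p1 = 0.12, the square bracket is 0.12/0.27 − 0.88/1.73 = 0.444 − 0.509 = −0.064. So D_A = −0.03F + 0.0019ac. About 0.2% of the excess adverse-effect cost survives in the modelled difference; the rest cancels.

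**3. Results, £ per person, active minus control**

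| Excess a | Cost c | By allocation | From fracture status |
|---|---|---|---|
| 1% | £50 | −29.50 | −30.00 |
| 2.4% | £100 | −27.60 | −30.00 |
| 2.4% | £300 | −22.80 | −29.99 |
| 10% | £300 | 0.00 | −29.94 |

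With equal fracture rates (15% and 15%), the fracture-status method returns exactly £0, whatever a and c are. The amount missed is essentially a × c.

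**4. Size for adverse effects, per 1000 allocated.** This treats the review rates as if they were wholly excess, and assumes £20 to £80 per gastrointestinal case and £500 to £2,000 per renal event.
- Low: 24 × £20 + 1 × £500 = £980.
- High: 24 × £80 + 1 × £2,000 = £3,920.

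At the wider £50 to £300 per gastrointestinal case, that part alone is 24 × £50 = £1,200 to 24 × £300 = £7,200.

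**5. For scale.** The mean hip price is (£4018 + £4808)/2 = £4413. Twenty fewer hip fractures per 1000 give 20 × £4413 = £88,260. The £980 to £3,920 is 1.1% to 4.4% of that. The share of the full saving would be lower, because this denominator leaves out other fractures and long-term care.

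**The case against.** **The text does not say fracture status is the only input.** It makes the fracture groups a foundation for the modelling and does not exclude others. The questionnaire (Appendix 12) is not shown, and 6.5 says the evaluation's type and extent depend on the clinical result. This stands: exclusivity is inferred. But 6.5 does fix how survey data reach the study groups, and it names nothing besides fracture. That is a stated method, not a detail left for later.

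**Not all of the cost plan is tied to fracture.** The general unit costs and the four-monthly care location are unrestricted, and admissions and residence are outcomes analysed as randomised. This stands too, so it would be wrong to say that every cost in 6.5 runs through fracture. Still, 6.5 does not say these items will be compared by allocation as costs, and it names no price for a non-fracture admission.

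**Adverse effects are not literally free.** Surveyed care for them enters the pooled means, and health loss can reach the QALY side through EQ-5D and SF-12, which go to everyone. What is lost is the between-group cost difference.

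**Two stronger readings are tempting and not supported.**
- A reader might infer that the plan would report no resource difference in a trial with no fracture benefit, and so mislead. The arithmetic is right, but all three scenarios in 6.5 suppose that some regimen reduces fractures. No ratio is promised otherwise.
- A reader might infer a large bias from non-fracture admissions. The protocol gives no admission rate, price or expected difference, and admissions could fall as well as rise. Suppose 300 to 900 admissions per 1000 and a 3% difference, that is 9 to 27 per 1000. With 2,000 per margin and Poisson counts, the standard error is √(2 × 0.3/2000) = 17 to √(2 × 0.9/2000) = 30 per 1000. The supposed difference is below one standard error.

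**Parsimony.** Section 6.5 wants little economic data collection. A comparison by allocation asks participants for nothing more.

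**Conclusion.** The point holds as one of method, and it is minor. As written, 6.5 states no comparison of survey resource use by allocation, and its modelling route almost removes any between-group difference that does not act through fracture. For adverse effects the bias favours the supplements in scenarios (ii) and (iii), provided the tablets do cause an excess. For other non-fracture care neither size nor direction can be given.

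The adverse-effect part is about £1,000 to £4,000 per 1000 allocated. This rests on assumed unit costs and on review rates that section 8.3 does not present as an excess over control, so 24 and 1 per 1000 are ceilings. Section 8.3 itself expects adverse effects to be very uncommon. The omission would matter most if the fracture benefit were small, or for the increment from adding calcium.

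**What to change.** Keep the fracture-status model in 6.5 for extrapolation beyond the trial. Add a within-trial comparison by randomised group, on the factorial margins, of priced survey resource use, all recorded admissions and location of care. Show it with confidence intervals beside the modelled estimate. Name a price source for non-fracture admissions.

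The cost is a few sentences and some extra analysis of data already planned for all participants. The direct comparison will be noisier than the modelled one, and a single mid-trial survey covers only part of follow-up. It should therefore be read alongside the model rather than in place of it.
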